12.6 Analysis of the Exploratory Endpoints

The exploratory endpoints change from baseline in number of monthly headache episodes and migraine attacks for Weeks 1-12 and Weeks 13-24 will be evaluated similarly to the primary endpoint (see Section 12.3.2).

All the exploratory endpoints related to the eDiary or scales endpoints after Week 24 will be analysed similarly to what is described in Section 12.5, for inclusion into the *addendum CSR*.

13 Safety

13.1 Adverse Events

13.1.1 General Methodology for Adverse Events

Unless otherwise specified, tables, graphs, and listings will be based on the APTS for the Placebo-controlled Period and the APTS_LT for the Extension Period.

All the tables and graphs will be presented by treatment group for the Placebo-controlled Period and by treatment sequence group for the Extension Period, unless otherwise specified.

Tables by preferred term and tables by system organ class (SOC) and preferred term will be sorted in descending order based on the percentages of patients with these adverse events in the eptinezumab 300 mg dose group.

Unless otherwise specified, the summaries of adverse events will include the number and percentage of patients with an adverse event. In tables displaying SOC or preferred terms, patients are counted only once within each SOC or preferred term.

Listings of adverse events will be sorted by site, treatment group, patient screening number, and adverse event start date, and include preferred term, investigator term, adverse event start date, the date of first IMP infusion, the date and time of the latest IMP infusion prior to the adverse event, the time since latest IMP infusion, duration of the adverse event, date of death, action taken, causality, intensity, seriousness, and outcome. For adverse events that change in intensity, each intensity will be included. In listings of adverse events, start or stop dates will be displayed as collected also in case of partially or completely missing dates.

13.1.2 Coding of Adverse Events

Adverse events will be coded using MedDRA, Version 23.0 or later.

13.1.3 Classification of Adverse Events

Adverse events will be classified according to the time of onset of the adverse event:

- *pre-treatment adverse event* an adverse event that starts on or after the date the patient signed the *Informed Consent Form* and prior to the date and time of first dose of IMP
- *treatment-emergent adverse event* (TEAE) an adverse event that starts or increases in intensity during or after administration of the first dose of IMP

For handling of adverse events with incomplete start dates to facilitate this classification, see Section 19.3.5. Note that adverse events with incomplete start dates will be classified as treatment-emergent simply if the imputed start date is on or after the date of first IMP infusion, since the start time of the adverse event will not be imputed, unless the investigator in such a case has assessed that the causality to IMP is "Not Related - Prior to IMP". An adverse event is considered causally related to the use of the IMP when the causality assessment by the investigator is *probable* or *possible*. If the causality assessment is missing, the adverse event is considered causally related.

13.1.4 Allocation of TEAEs to Treatment Periods

TEAEs will be allocated to treatment periods according to the time of onset of the adverse event:

- *TEAE in the Placebo-controlled Period* a TEAE that starts before the date and time of the start of Visit 8 IMP infusion
- *TEAE in the Extension Period* a TEAE that starts during or after administration of Visit 8 IMP infusion

For allocation of TEAEs to treatment periods, the same rule for imputed dates as specified above (in Section 13.1.3) applies, i.e. for incomplete start dates, only the imputed start date and not the time (which will not be imputed) of the adverse event will be taken into account in the allocation of the TEAE to periods.

If an adverse event starts on the day of the Visit 8 IMP infusion but with an unknown start time, the adverse event will be classified as treatment-emergent in the Placebo-controlled period.

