10.3 Recording Adverse Events

Adverse events (including pre-treatment adverse events) must be recorded on an *Adverse Event Form*. The investigator must provide information on the adverse event, preferably with a diagnosis, or at least with signs and symptoms; start and stop dates (and start and stop time if the adverse event lasts less than 24 hours); intensity; causal relationship to the IMP; action taken; and outcome. If the adverse event is not related to the IMP, an alternative aetiology must be recorded, if available. If the adverse event is an overdose, the nature of the overdose must be stated (for example, medication error, accidental overdose, or intentional overdose). If the intensity changes during the course of the adverse event, this must be recorded on the *AE Intensity Log*.

If the adverse event is *serious*, this must be indicated on the *Adverse Event Form*. Furthermore, the investigator must fill out a *Serious Adverse Event Form* and report the SAE to Lundbeck immediately (within 24 hours) after becoming aware of it (see section 10.4).

If individual adverse events are later linked to a specific diagnosis, the diagnosis should be reported and linked to the previously reported adverse events.

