The patient will receive IMP starting from the Baseline Visit to follow a dosing schedule with IV infusions every 12 weeks with either eptinezumab or placebo over 30 minutes (+15).

At Visit 8 patients will enter the Extension Period. Patients who were assigned to placebo in the Placebo-controlled Period will be randomly allocated to one of two treatment groups: eptinezumab 300 mg or eptinezumab 100 mg with a ratio of 1:1. Patients assigned to eptinezumab 300 mg or eptinezumab 100 mg in the Placebo-controlled Period will continue on their original assignments.

An overview of the study is presented in Panel 2 and the scheduled study procedures and assessments are summarized in Appendix II. See also the *Clinical Study Protocol* for further details on the study design.

Panel 2 Study Design

For patients who withdraw, except for those who withdraw their consent, a Withdrawal Visit will be scheduled 12 weeks after the last dose of IMP. The withdrawal visit will include Safety Follow-up evaluations and will therefore also serve as a Safety Follow-up Visit.

For patients who withdraw prior to Week 24 the Withdrawal Visit will allow for eDiary closeout and for a final assessment of scales not based on the eDiary. Patients are expected to complete their eDiary until this Withdrawal Visit unless the patient withdraws consent.

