13.1.5 Presentation of Adverse Events

A listing of all adverse events starting at or after entering the Extension Period, including a flag for TEAEs will be included in the *addendum to CSR* based on the APTS_LT.

A similar listing of all adverse events occurring before entering the Extension Period will be produced for the *CSR* based on APRS.

For each period, an overview of the numbers and percentages of patients with TEAEs, serious adverse events (SAEs), TEAEs leading to infusion interruption, TEAEs leading to withdrawal, and of patients who died will be provided based on the APTS/APTS_LT. For TEAEs, SAEs, and TEAEs leading to withdrawal, the total number of events will be included.

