19.4.2 Changes in Intensity or Seriousness of Adverse Events

An adverse event that changes in intensity in a period will contribute to the count of events as a single event.

In summaries of adverse events presented by intensity, the maximum intensity of the adverse event will be used. The maximum intensity is searched for in events with changes, as well as over repeated events based on the preferred term. Adverse events for which information on intensity is missing will be classified as *severe*.

Adverse events with an update in seriousness will be included in ADaM with only one row. For such an event, the start date of the serious adverse event will be set to the start date of the original event. This means that an adverse event with a start date prior to first infusion of IMP (i.e. not classified as treatment-emergent) that is registered as serious after first IMP infusion will still not be classified as treatment-emergent, unless a change in intensity is taking place after first IMP infusion as well.

Adverse events for which information on seriousness is missing will be classified as serious.

References

- 1. International Headache Society (IHS), Headache Classification Committee. The International Classification of Headache Disorders, 3rd edition 2018 (ICHD-3 2018).
- 2. Robinson LD and Jewell NP. Some surprising results about covariate adjustment in logistic regression models. International Statistical Review. 1991; 59: 227-240.
- 4. Little R and Yau L. Intent-to-treat analysis for longitudinal studies with drop-outs. Biometrics. 1996; 52: 1324-1333.
- 5. Rubin, DB. Multiple imputation for nonresponse in surveys. New York: Wiley; 1997.
- 6. United States Food and Drug Administration (US FDA). Guidance for Industry: Drug-induced liver injury: premarketing clinical evaluation. July 2009.

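### SAP 13.1.4 allocates TEAEs to periods by onset alone, so events that worsen or become serious after a placebo patient's first eptinezumab infusion are left out of the Extension AE tables

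*SAP*

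**What the plan says.** SAP 13.1.3 defines a TEAE as "an adverse event that starts or increases in intensity during or after administration of the first dose of IMP". The reference point is the first dose of any IMP, which for a placebo patient is placebo at Visit 2.

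SAP 13.1.4 then assigns periods: "TEAEs will be allocated to treatment periods according to the time of onset of the adverse event". The Placebo-controlled Period takes "a TEAE that starts before the date and time of the start of Visit 8 IMP infusion" and the Extension Period takes "a TEAE that starts during or after administration of Visit 8 IMP infusion". Neither limb mentions an increase in intensity.

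SAP section 2 fixes the start of eptinezumab for the placebo arm. At Visit 8, "Patients who were assigned to placebo in the Placebo-controlled Period will be randomly allocated to one of two treatment groups", 100 mg or 300 mg.

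SAP 19.4.2 adds two rules. Tables by intensity use the maximum intensity of the event, with no stated limit to the period. An event whose seriousness is updated stays on one row, and "the start date of the serious adverse event will be set to the start date of the original event".

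The main Extension listing in SAP 13.1.5 also works by start: "A listing of all adverse events starting at or after entering the Extension Period". Protocol 16.9.1 leaves the study periods for TEAEs to the SAP, so the protocol does not settle the matter.

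**The concern.** The study has two changes of exposure: no drug to IMP at Visit 2, and, for placebo patients, placebo to eptinezumab at Visit 8. The SAP treats worsening as treatment-emergent at the first and is silent on it at the second. Yet the second is when former placebo patients first meet the active drug, and long-term safety and tolerability of eptinezumab is a stated objective.

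If the rule is followed as written, a condition that was present on placebo and deteriorates on eptinezumab is absent from the Extension TEAE and intensity tables. One that becomes serious is absent from the Extension treatment-emergent SAE tables. One that causes withdrawal can be tabulated in the wrong period, so the table of TEAEs leading to withdrawal and the disposition table need not agree.

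**Working it through.** The plan states no figure on this point, so there is nothing to reproduce. The check is to apply the rules as written to test events in one placebo patient.

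Inputs: Visit 2 infusion = day 0 and Visit 8 infusion = day 168 (nominal days, SAP 19.2.2); TEAE status from 13.1.3; period from 13.1.4; seriousness dating from 19.4.2; period of withdrawal from 4.3.

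Rule as written: the event is a TEAE if onset ≥ day 0 or any worsening falls on or after day 0. If it is a TEAE, it goes to the Placebo-controlled Period when onset < day 168 and to the Extension otherwise.

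| Event | SAP as written | By date of the change |
|---|---|---|
| 1. New onset day 170 | Extension | Extension |
| 2. Onset day 150, worsens day 175 | Placebo-controlled | Both periods |
| 3. Onset day 150, serious day 175 | Placebo-controlled | Both periods |
| 4. Onset day 150, leads to withdrawal day 180 | Placebo-controlled | Both periods |
| 5. Onset in screening, first worsens day 175 | Placebo-controlled, on the literal wording | Extension |
| 6. Onset in screening, serious day 175, no change in intensity | Not a TEAE | Extension |

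None of the five crossing events (2 to 6) is an Extension TEAE. Their strength differs.

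- Event 3 is the firmest, because 19.4.2 states the back-dating outright.
- Event 2 follows from 13.1.4 naming only the start of the event.
- In event 4, SAP 4.3 calls the patient completed in the Placebo-controlled Period and withdrawn in the Extension, while 13.1.4 puts the causative TEAE in the Placebo-controlled Period.
- Event 5 becomes a TEAE only through a change after Visit 8, yet its onset places it before Visit 8.
- Event 6 follows a rule the SAP spells out for the first dose, so it is a consequence of a stated choice.

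Scale, from the planned 280 placebo patients re-randomized 1:1, if all enter the Extension:

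- sequence arm: 280 / 2 = 140
- one patient in the placebo arm: 1 / 280 = 0.36 percentage points
- one patient in a sequence arm: 1 / 140 = 0.71 percentage points

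The documents give no rate of such events. Assuming 0.5% to 5% of placebo patients, the count is 0.005 × 280 = 1.4 to 0.05 × 280 = 14, or 0.7 to 7 per sequence arm.

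**The case against.** The best reply is that the SAP is incomplete here rather than decided. Sections 13.1.3 and 13.1.4 share the same lead-in about time of onset, and 13.1.3 counts worsening under it. Section 13.1.1 shows every intensity in listings, 19.3.5 imputes incomplete intensity-change dates with the start-date algorithm, and 19.4.2 speaks of intensity changes within a period. These point to dated intensity records. That stands as evidence of what may have been intended. But 13.1.3 had to add worsening explicitly, 13.1.4 does not, and no section allocates a change that crosses Visit 8.

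Three stronger readings are tempting and are not supported.

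- *The events vanish from all Extension outputs.* They do not. Extension withdrawals are tabulated and listed by reason (7.2). Deaths after entry bring a listing of all the patient's AEs (13.1.7). Patients with Extension PCS values or positive ADA results have all their AEs listed (13.2, 13.3.2). The Extension listings of SAEs, AEs leading to withdrawal or infusion interruption, and AESIs (13.1.8 to 13.1.11) are worded by occurrence rather than start, and may capture some of these events.
- *The placebo column of the CSR is inflated.* The Placebo-controlled Period is locked and reported first (Protocol 3.1; SAP 2.1). A change after Visit 8 can reach that column only if it is in the dataset used, so loss is likelier than inflation.
- *All 840 patients are affected in the same way.* About 560 are already on eptinezumab before Visit 8, so for them there is no placebo-to-active crossing.

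Onset-based allocation also has the merit of counting each event once, and the tables are descriptive. Single-row handling of seriousness is deliberate: 19.4.2 says that an event with onset before the first dose that later becomes serious stays non-treatment-emergent unless its intensity also changes. That limits the remedy but does not remove the gap.

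**Conclusion.** The point holds for the Extension AE summary tables and the 13.1.5 all-AE listing. Followed as written, the SAP leaves out worsening of a placebo-onset event after the first eptinezumab infusion and keeps an event that becomes serious then out of the Extension treatment-emergent SAE tables. It can also tabulate a TEAE that led to withdrawal in a period where the patient counts as completed. If the later data are in the dataset, the maximum-intensity rule could in addition show an intensity reached on eptinezumab under placebo.

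The size cannot be derived from the documents. Each such patient is worth 0.36 points of the placebo arm or 0.71 points of a sequence arm, on the assumption that all 280 enter the Extension. Any total rests on an assumed rate. The comparison of new-onset events before Visit 8 is unaffected, and no efficacy or type 1 error conclusion changes.

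**What to change.** Amend the SAP in five places.

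1. In 13.1.4, define an Extension Period TEAE as one that starts or increases in intensity during or after the Visit 8 infusion. This matches the two limbs of 13.1.3.
2. In 19.4.2, limit maximum intensity to the period being summarized.
3. In 13.1.9, tabulate TEAEs leading to withdrawal in the period of withdrawal defined in 4.3.
4. In 13.1.5, extend the Extension listing to events that worsen or become serious after Visit 8.
5. If seriousness changes are to count in the Extension SAE tables, amend the one-row, original-start-date rule in 19.4.2 at the same time, and state how the new rule relates to the first-dose rule there. Adding seriousness to 13.1.4 alone would contradict 19.4.2 and would go beyond 13.1.3, which has no seriousness limb.

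No new intensity data are needed. Protocol 10.3 already requires it: "If the intensity changes during the course of the adverse event, this must be recorded on the" AE Intensity Log. SAP 19.3.5 already imputes incomplete change dates. The cost is SAP wording and an extra dataset row for each qualifying event. The downside is that one event can appear in both periods, and Extension incidence becomes slightly less favourable.

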- g Assessments involving interviews and scales must be done before the infusions. All efficacy and pharmacoeconomic assessments are PROs. PROs which are scheduled in alignment with a clinic visit can be completed in the clinic or in the remote setting within 3 days prior to the scheduled clinic visit date. Additionally, PGIC (at Week 4 only), HIT-6, EQ-5D-5L, HCRU, WPAI which are scheduled in alignment with a phone contact must be completed in the remote setting and can be completed on the day or within 3 days prior to the scheduled phone contact date.
- h The eDiary assessments will be completed in the remote setting on a daily basis.
- i At the Screening Visit, the patient must be assisted with the provisioning and training of the eDiary and training of efficacy and pharmacoeconomic assessments (PROs). Details will be provided in a separate user manual.
- j The eDiary closeout will take place at the Completion/Withdrawal Visit, while the patient is at site. Details will be provided in a separate user manual.

- k The patients will be contacted via phone every 4 weeks between infusion visits for eDiary compliance check, to ensure that selected assessments have been completed and for collection of relevant information such as AEs and concomitant medication.
- 1 PGIC at Week 4 must be completed in the remote setting.
- m At infusion visits, infusion related reactions (IRRs) must be checked as part of the overall AE collection, after infusion and before the patient is discharged from the site.
- n At infusion visits, physical examination, ECG, blood sampling (for clinical safety laboratory tests, ADA and biobank) and urine samples (for clinical safety laboratory tests and pregnancy) must be conducted before infusion. AEs, vital signs including body temperature should be checked before and after infusion.
- o The C-SSRS will be administered by the authorized rater at the clinic and prior to infusion.
- p Patients who test positive for ADA at the Completion Visit will be asked to provide up to two additional blood samples for immunogenicity testing at 12-week intervals for up to 24 weeks.
- q At infusion visits, patients must be monitored for a period of 1 hour from the end-of-infusion. Patients will be requested to stay longer should the investigator determine this is clinically warranted.

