16.7 Exposure

Number of infusions in the Placebo-controlled Period (infusions at Visit 2 and visit 5), and number of infusions in the Extension Period (infusions at Visit 8, Visit 11, Visit 14, and Visit 17) will be summarized.

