4.1 Definition of Periods

The study consists of the following periods:

- *Screening Period* (28-30 days): Starts at the Screening Visit and continues up to start of Visit 2 IMP infusion
- *Placebo-Controlled Period*: Starts at start of Visit 2 IMP infusion and continues up to start of Visit 8 IMP infusion
- *Extension Period*: Starts at start of Visit 8 IMP infusion and continues up to and including Visit 20

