13.1.6 Presentation of Treatment-emergent Adverse Events

The following summaries will be provided for the Placebo-controlled Period and for the Extension Period:

- TEAEs by SOC and preferred term
- TEAEs by preferred term
- TEAEs by sex and preferred term
- TEAEs with an incidence $\geq 2\%$ in any treatment group by preferred term
- causally related TEAEs by SOC and preferred term
- TEAEs by intensity (*mild/moderate/severe*), SOC, and preferred term

- causally related TEAEs by intensity, SOC, and preferred term
- TEAEs occurring on the day of dosing after infusion start by SOC and preferred term (this includes day of V2 and V5 infusion for the Placebo-controlled Period and day of V8, V11, V14, and V17 infusion for the Extension Period)

The summaries will be provided for the APTS for the Placebo-controlled Period and for APTS_LT for the Extension Period.

For the Extension Period, the two tables summarizing all TEAEs by SOC and preferred term and all TEAEs by preferred term will include two additional columns displaying the totals for eptinezumab 100 mg and eptinezumab 300 mg.

For TEAEs occurring on the day of dosing after infusion start, TEAEs with missing start times will also be included.

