13.1.10 Presentation of Adverse Events Leading to Study Drug Infusion Interruption

All AEs leading to study drug infusion interruption before entering the Extension Period will be listed for the APRS for inclusion in the *CSR*.

All AEs leading to study drug infusion interruption occurring at or after entering the Extension Period will be listed for the APTS_LT for inclusion in the *addendum to CSR*.

TEAEs leading to study drug infusion interruption will be summarized for the Placebocontrolled Period based on APTS and for the Extension Period based on APTS_LT by:

- SOC and preferred term
- preferred term

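### Untimed adverse events on the Visit 8 infusion day are counted in the Placebo-controlled Period, so an event after a placebo patient's first eptinezumab dose can be reported under placebo

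*SAP*

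**What the plan says.** SAP 4.1 ends the Placebo-controlled Period at the start of the Visit 8 infusion. It defines the Extension Period thus: "Starts at start of Visit 8 IMP infusion and continues up to and including Visit 20". The two bullets in SAP 13.1.4 follow that boundary: onset before the infusion belongs to the first period, onset during or after it to the second.

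The last sentence of 13.1.4 covers an event whose date is the Visit 8 infusion day but whose time is not known: "with an unknown start time, the adverse event will be classified as treatment-emergent in the Placebo-controlled period". It makes no distinction by arm, causality or type of event.

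SAP 13.1.6 defines a separate table of TEAEs on the day of dosing after infusion start. For the Placebo-controlled Period it covers the Visit 2 and Visit 5 days. The other part covers the "day of V8, V11, V14, and V17 infusion for the Extension Period". It adds: "For TEAEs occurring on the day of dosing after infusion start, TEAEs with missing start times will also be included".

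Protocol 10.3 asks the investigator for "start and stop dates (and start and stop time if the adverse event lasts less than 24 hours"). A longer event may carry a date only.

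**The concern.** SAP section 2 re-randomizes placebo patients to eptinezumab at Visit 8, so that infusion is their first active dose. SAP 4.4 tabulates adverse events by actual treatment, set separately for each period. A placebo patient's event that 13.1.4 sends to the Placebo-controlled Period therefore appears in the placebo column, even if it followed eptinezumab.

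The Placebo-controlled Period is the only placebo-controlled safety comparison in the trial. Protocol 16.7 describes its exposure as "Number of infusions in the Placebo-controlled Period (infusions at Visit 2 and visit 5"). The rule adds untimed events from a third dosing day, on which every dosed patient in every arm receives eptinezumab. For patients already on eptinezumab, untimed third-dose events enter the controlled period in the same way.

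The rule also reaches the special tables. SAP 13.1.10 states: "TEAEs leading to study drug infusion interruption will be summarized for the Placebocontrolled Period based on APTS". An untimed event that interrupted the Visit 8 infusion can land in that table, although the infusion belongs to the Extension Period. The withdrawal tables have a similar problem. Under SAP 4.3 a patient who withdraws after the Visit 8 infusion has completed the Placebo-controlled Period. Under 13.1.4 an untimed Visit 8-day event leading to that withdrawal still counts in the Placebo-controlled Period.

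**Working it through.** The plan gives no figure to reproduce, so the check is mainly a reading of the rules, followed by arithmetic for scale.

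**One event through the rules.** Take a placebo patient who receives the Visit 8 infusion. An event starts later that day, lasts two days, and has a date but no time, as Protocol 10.3 allows.

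| Provision | Where the event goes |
|---|---|
| SAP 4.1 and the 13.1.4 bullets, true onset known | Extension Period |
| SAP 13.1.4, last sentence | Placebo-controlled Period, placebo column |
| SAP 13.1.6, applied by date | Extension day-of-dosing table |
| SAP 13.1.6, applied after 13.1.4 | neither day-of-dosing table |

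On the third row, the event is in the Extension day-of-dosing table but not in the Extension table of all TEAEs, of which that table should be a subset. On the fourth row, it is not an Extension TEAE, and the Placebo-controlled part covers only Visits 2 and 5, so it drops out of both. Two programmers could follow the SAP and produce different tables.

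**Scale, from the planned 280 patients per group.**

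- One placebo patient: 1/280 = 0.36 percentage points.
- The table of TEAEs with incidence of at least 2% needs 6 patients: 5/280 = 1.79%, 6/280 = 2.14%. One moved patient can take a preferred term across the cut-off if no other group already reaches 2%.

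**Illustration under assumptions.** None of these inputs is in the documents. Let r be the share of each arm dosed at Visit 8 (0.90 to 0.95, or 252 to 266 of 280). Let p be the share of dosed patients with an untimed Visit 8-day event that in truth followed the infusion. Let b be the true TEAE rate of interest in the controlled period (5% eptinezumab, 3% placebo, a difference of 2.0 points). If untimed events are independent of other TEAEs:

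observed rate = b + r × p × (1 − b)

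| p placebo | p eptinezumab | Difference, r = 0.90 | Difference, r = 0.95 |
|---|---|---|---|
| 1% | 1% | 1.98 | 1.98 |
| 2% | 2% | 1.96 | 1.96 |
| 2% | 1% | 1.11 | 1.06 |
| 1% | 2% | 2.84 | 2.88 |

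For example, the third row at r = 0.90 is (5 + 0.90 × 1 × 0.95) − (3 + 0.90 × 2 × 0.97) = 5.855 − 4.746 = 1.11 points. Equal shares hardly move the difference. Unequal shares move it by about 0.8 to 0.9 points in either direction.

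**The case against.** The strongest reply is that this is a tie-break: without a time, any default misplaces some events, and the SAP has at least pre-specified one. Protocol Panel 2, footnote n, says "AEs, vital signs including body temperature should be checked before and after infusion", so some untimed events will indeed precede the infusion. That stands, and it means misallocation is possible rather than certain for any one event. It does not rescue the rule, because 13.1.6 already treats the same day as an Extension dosing day and takes missing times as after infusion start. Reading 13.1.4 first removes the double placement but leaves the event in neither day-of-dosing table.

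Other limits also stand. Timed events are allocated correctly. Events under 24 hours should have a time, so most short infusion reactions ought to be unaffected, and an untimed event that interrupted an infusion is likely to be rare. The rule concerns a known Visit 8 date; incomplete dates are handled in the preceding paragraph of 13.1.4 by imputed date. The same-day conventions in 13.1.3 for the first dose and in 19.3.4 for medications run the other way, but they cover different situations and do not contradict this rule. The shares in the illustration are assumed, and with equal shares the effect is negligible. Affected events remain in the main TEAE tables and in the listings, and no efficacy analysis or step of the testing strategy is touched.

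**Conclusion.** The concern holds. As written, SAP 13.1.4 can put an event that followed a placebo patient's first eptinezumab dose in the placebo column, and it conflicts with 13.1.6 over the same day. This follows from the text and needs no assumption about rates.

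The size cannot be derived from the documents, because they give no frequency of untimed Visit 8-day events. The net direction is also open, since it depends on the untimed share in each arm. That is a reason to correct the rule and show its effect, not to call it conservative. It should be fixed, but it bears only on the safety tables.

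**What to change.** In SAP 13.1.4, allocate events that start on the Visit 8 infusion date with unknown time to the Extension Period. Except those where recorded information shows onset before that infusion, for example an event reported at the pre-infusion check. If no such field is collected, apply the rule without the exception.

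In 13.1.6, state that period allocation follows 13.1.4, so that an untimed Visit 8-day event appears once, in the Extension day-of-dosing table. Repeat the Placebo-controlled TEAE table under the other allocation. Flag the affected events in the existing listings, which under 13.1.1 already carry the event start date and the date and time of the latest infusion.

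The cost is one sentence, one cross-reference, one condition in the derivation of the event period, one repeated table and one flag. No new data are collected. The downside is that some events that began before the infusion may be counted in the Extension Period, under eptinezumab; the repeated table shows how much that matters.
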